Appendix 5.	Gilead Grading Scale for Severity of Adverse Events and Laboratory Abnormalities	106

Appendix 6.	HIV Testing Algorithm	128
Appendix 7.	HIV Infection Endpoint Definition.....	129
Appendix 8.	Pandemic Risk Assessment and Mitigation Plan	130

LIST OF IN-TEXT TABLES

Table 5-1.	Prior and Concomitant Medications	42
Table 8-1.	Efficacy Information from Truvada as PrEP in MSMs	86

LIST OF IN-TEXT FIGURES

Figure 1-1.	Design of Study PC-412-2001 of F/TAF for PrEP in Rhesus Macaques.....	21
Figure 1-2.	Plasma RNA and Serology Results from Study PC-412-2001 of F/TAF for PrEP in Rhesus Macaques	22
Figure 3-1.	Study Schema	35

PROTOCOL SYNOPSIS

Gilead Sciences, Inc.
[name]
[name]

Study Title:	A Phase 3, Randomized, Double-blind Study to Evaluate the Safety and Efficacy of Emtricitabine and Tenofovir Alafenamide (F/TAF) Fixed-Dose Combination Once Daily for Pre-Exposure Prophylaxis in Men and Transgender Women Who Have Sex with Men and Are At Risk of HIV-1 Infection
IND Number: EudraCT Number:	127728 2016-001399-31
Study Centers Planned:	Approximately 100 centers in North America and Europe
Objectives:	
The primary objective of this study is:
 
• To assess the rates of HIV-1 infection in men who have sex with men (MSM) and transgender women (TGW) who have sex with men who are administered daily emtricitabine/tenofovir alafenamide (F/TAF) or emtricitabine/tenofovir disoproxil fumarate (F/TDF) with a minimum follow up of 48 weeks and at least 50% of the participants have 96 weeks of follow up after randomization 
The secondary objectives of this study are:
 
• To compare bone safety between the treatments as determined by dual-energy X-ray absorptiometry (DXA) tests of hip and spine bone mineral density (BMD) in a subset of participants at Week 48 and Week 96 in the blinded phase• To compare renal safety between the treatments as determined by urine retinol-binding protein (RBP) to creatinine ratio, urine beta-2-microglobulin to creatinine ratio, urine protein to creatinine ratio (UPCR), and serum creatinine at Week 48 and Week 96 in the blinded phase• To assess the rates of HIV-1 infection in MSM and TGW who have sex with men who are administered daily F/TAF or F/TDF when all participants have 96 weeks of follow up after randomization• To compare the general safety between the treatments

	
CCI [REDACTED]
 
■ [REDACTED]■ [REDACTED]■ [REDACTED]■ [REDACTED]■ [REDACTED]

Study Design:
	
Randomized, double-blind comparison of the safety and efficacy of F/TAF versus F/TDF administered orally once daily.
 
All participants must meet eligibility criteria in order to receive treatment in the study. Once randomized to receive treatment in the study, all participants must return to the study center for required visits at Weeks 4, 12, and every 12 weeks thereafter.
 
All participants will remain blinded to study drug for at least 96 weeks. The primary endpoint data will be collected and analyzed after all participants have a minimum follow up of 48 weeks and at least 50% of participants have 96 weeks of follow up after randomization.
 
Once all participants have at least 96 weeks of follow up after randomization and upon notification by Gilead, all participants will return to the study center for an end of blinded treatment phase visit (may coincide with their next scheduled visit).
 
Participants who are still on blinded study drug at the end of blinded treatment phase visit will be offered entry into the OL phase of the study. Participants who continue participation in the OL phase will be administered F/TAF once daily and will return to the study center for visits every 12 weeks. CCI [REDACTED]
 
[REDACTED] Participants who have discontinued study drug prior to the end of blinded treatment phase visit due to HIV infection will be eligible to continue participation in the OL phase, but will not be administered F/TAF once daily. From

	
OL Week 48, participants who acquire HIV must complete the early study drug discontinuation (ESDD) visit and discontinue the study at the 30-Day Follow-up visit, 30 days after the last dose of study drug. Participants who have discontinued study drug for any other reason prior to the end of blinded treatment phase visit will not be eligible to participate in the OL Phase.
 
CCI [REDACTED]

Number of Participants Planned:	5000
Target Population:	MSM and TGW (male at birth) who are at risk of HIV-1 infection through sexual exposure with other men
Duration of Treatment:	
Blinded Phase:
 
Participants will receive study drug for at least 96 weeks. After completing the Week 96 visit, all participants will continue to take their blinded study drug and attend visits every 12 weeks until the last participant reaches Week 96. All participants will return to the study center for an end of blinded treatment phase visit (may coincide with their next scheduled visit) upon notification by Gilead.
 
CCI [REDACTED]
 
Open-Label Phase:
 
Participants will receive OL F/TAF for up to 96 weeks and will continue OL study visits every 12 weeks. From OL Week 48, participants who acquire HIV must complete the ESDD visit and discontinue the study at the 30-Day Follow-up visit 30 days after the last dose of study drug.
 
Open-Label Extension Phase:
 
CCI [REDACTED]
 
Participants who have been diagnosed and confirmed as HIV positive during this phase must complete the ESDD visit and discontinue the study at the 30-Day Follow-up visit, 30 days after the last dose of study drug.


Diagnosis and Main Eligibility Criteria:
	
 • HIV-1 negative status • MSM or TGW (male at birth) who have at least one of the following: 
 a) condomless anal intercourse with at least 2 unique male partners in the past 12 weeks (partners must be either HIV-infected or of unknown HIV status) b) documented history of syphilis in the past 24 weeks c) documented history of rectal gonorrhea or chlamydia in the past 24 weeks • Age \geq 18 years • No suspected or known active, serious infection(s) • Estimated glomerular filtration rate \geq 60 mL/min according to the Cockcroft-Gault formula • Adequate liver and hematologic function: • Aspartate aminotransferase (AST) and alanine aminotransferase (ALT) \leq 2.5 \times upper limit of normal (ULN) and total bilirubin \leq 1.5 mg/dL, or normal direct bilirubin • Absolute neutrophil count \geq 1000/mm³, platelets \geq 75,000/mm³, and hemoglobin \geq 10 g/dL • Have not received investigational agents for the treatment or prevention of HIV-1 infection in the 30 days prior to screening • No evidence of acute viral hepatitis A, B or C, and no evidence of chronic hepatitis B virus infection. Participants found to be susceptible to hepatitis B virus (HBV) infection should be referred for HBV vaccination. Participants found to be positive for hepatitis C virus (HCV) must not have active infection or must have completed treatment and achieved a sustained virologic response • No history of osteoporosis or bone fragility fractures

Study Procedures/ Frequency:
	
Screening Visit Upon providing written informed consent, participants will be evaluated for eligibility at the screening visit, including medical history review, concomitant medication review, complete physical examination including height, weight, and vital signs, sexually transmitted infection (STI) testing for gonorrhea, chlamydia, and syphilis, fourth generation rapid HIV-1 antibody (Ab)/antigen (Ag) or third generation rapid HIV-1 Ab test, HIV Ab/Ag testing, HIV-1 RNA testing if applicable, Hepatitis B testing, Hepatitis C testing, clinical laboratory assessments for blood and urine samples,

computer-assisted self-interview (CASI) for: recent sexual risk events; interest in using PrEP; self-identification of transgender status; education and employment history; and use of tobacco and recreational drugs, and risk reduction counseling including provision of condoms.

Prior to the Day 1 visit and randomization, the investigator will review the screening assessments to confirm eligibility. The Day 1 visit must occur within 30 days after the screening visit.

Blinded Treatment Phase

During the blinded treatment phase, participants will be seen at the study center for visits at Day 1, Weeks 4, 12, 24, and every 12 weeks thereafter until the end of blinded treatment phase visit.

At the Day 1 visit, participants will be assessed with fourth generation rapid HIV-1 Ab/Ag or third generation rapid HIV-1 Ab test, HIV-1 RNA if applicable, adverse event (AE) and concomitant medication review, targeted physical examination and vital signs if applicable, CASI, and adherence and risk reduction counseling including provision of condoms. CCI

At all other study visits during the blinded treatment phase, participants will be assessed with targeted physical examination (complete physical examination at Week 48 and 96), AE and concomitant medication review, vital signs if clinically indicated, weight, STI testing for gonorrhea, chlamydia, and syphilis, fourth generation rapid HIV-1 Ab/Ag or third generation rapid HIV-1 Ab test, HIV Ag/Ab testing, HIV-1 RNA testing if applicable, Hepatitis B testing (every 24 weeks), Hepatitis C testing (every 48 weeks), clinical laboratory assessments for blood and urine samples, plasma storage sample collection. CCI

If the participant discontinues study drug prior to the end of blinded treatment phase visit, the participant will be asked to return to the study center within 72 hours of stopping study drug for the ESDD visit. The participant will be asked to continue attending the scheduled study visits through the end of blinded treatment phase visit of the study. CCI

Participants who are still on study drug at the end of blinded treatment phase visit will be offered entry into the OL phase and OL

	
extension phase of the study. Participants who have discontinued study drug prior to the end of blinded treatment phase visit due to HIV infection will be eligible to continue participation in the OL phase up to OL Week 48, but will not be administered F/TAF once daily.
 
Open-Label Phase
 
During the OL phase, participants will be seen at the study center for visits every 12 weeks up to OL Week 96.
 
At all study visits during the OL phase, participants will be assessed with targeted physical examination (complete physical examination at OL Week 48), AE and concomitant medication review, vital signs if clinically indicated, weight, STI testing for gonorrhea, chlamydia, and syphilis, fourth generation rapid HIV-1 Ab/Ag or third generation rapid HIV-1 Ab test, HIV Ab/Ag testing, HIV-1 RNA testing if applicable, Hepatitis B testing (every 24 weeks), Hepatitis C testing (every 48 weeks), clinical laboratory assessments for blood and urine samples, plasma storage sample collection,
 
CCI
 
CCI
 
Throughout the study, participants may be asked to provide daily information on adherence and sexual risk events through the use of a diary. Participants may also receive periodic contacts to remind them to take their study drug and to provide any additional support needed.
 
Open-Label Extension Phase

	
During the OL extension phase, participants will be seen at the study center for visits every 12 weeks from OL Week 96 up to OL Week 408.
 
At all study visits during the OL extension phase, participants will be assessed with targeted physical examination (every 24 weeks), AE and concomitant medication review, vital signs (every 24 weeks), weight (every 24 weeks), STI testing for gonorrhea, chlamydia, and syphilis, at a minimum fourth generation rapid HIV-1 Ab/Ag or third generation rapid HIV-1 Ab test, HIV Ab/Ag testing, HIV-1 RNA testing if applicable, Hepatitis B testing (every 48 weeks), Hepatitis C testing (every 48 weeks), clinical laboratory assessments for blood samples, DBS collection and risk reduction counseling including provision of condoms.

Test Product, Dose, and Mode of Administration:
	
Blinded Phase: F/TAF fixed-dose combination (FDC) (200 mg emtricitabine/25 mg tenofovir alafenamide), administered orally once daily.
 
Open-Label and Open-Label Extension Phase:

	F/TAF FDC (200 mg emtricitabine/25 mg tenofovir alafenamide), administered orally once daily.
Reference Product, Dose, and Mode of Administration:	Blinded Phase: F/TDF FDC (200 mg emtricitabine/300 mg tenofovir disoproxil fumarate), administered orally once daily.
Criteria for Evaluation:	
Safety:	
 • Adverse events • Physical examinations, vital signs • Clinical laboratory tests of blood and urine • CCI • STI testing • Adherence measures including tablet collection, responses to adherence questions as part of the CASI, and FTC and/or TFV levels in the plasma or DBS
Efficacy:	
Incidence of HIV-1 infection defined by one or more of the following criteria of contributing HIV tests performed via central lab or local lab:
 
 1) Serologic evidence of seroconversion (reactive screening HIV Ag/Ab or Ab test, confirmed by the reactive HIV-1/HIV-2 differentiation assay), excluding HIV vaccinated participants, or 2) Virologic evidence of HIV-1 infection (positive qualitative HIV-1 RNA test or any detectable quantitative HIV-1 RNA test), or 3) Evidence of acute HIV-1 infection (reactive p24 Ag or positive qualitative or quantitative RNA, in the absence of reactive HIV-1 Ab results) 
Please refer to Appendix 7 for more details.

CCI	CCI
Risk Behavior Assessment:	Computer-Assisted Self-Interview (CASI) sexual risk event evaluation
Statistical Methods:	
The primary endpoint will be the incidence of HIV-1 infection (as defined above) per 100 person years (PY).
 
The primary analysis will occur when all participants have a minimum of 48 weeks of follow up and at least 50% of the participants have at least 96 weeks of follow up after randomization.

	
The primary analysis will consist of a non-inferiority evaluation of F/TAF versus F/TDF, with respect to the HIV-1 infection rate in PY as determined by rate ratios. It will be concluded that F/TAF is non-inferior to F/TDF if the upper bound of the 95% CI of the ratio between the two arms (F/TAF over F/TDF) is less than 1.62. The 95% CI will be constructed using a generalized model associated with a Poisson distribution and logarithmic link with the treatment group being the covariate. A sample size of 2500 in each arm provides at least 82% power to show F/TAF is non-inferior to F/TDF with respect to the HIV-1 infection rate, and assumes an HIV-1 infection rate of 1.44 per 100 PY in the F/TAF and F/TDF treatment arms, a 2-sided Type 1 error rate of 5%, and an average follow up of 2 years (ie, last participant has a minimum of 48 weeks of follow up and at least 50% of the participants have at least 96 weeks of follow up after randomization).
 
An independent data monitoring committee (IDMC) will be convened to primarily evaluate the safety of the treatments in this population. There are no prior plans to stop for efficacy or futility with formal boundaries. At a minimum, the IDMC will include 2 clinicians (including a chairperson), a biostatistician, a prevention expert, and a community member. The initial evaluation by the IDMC will occur either (1) after 50% of participants have completed Week 24 (or prematurely discontinued from the study drug) or (2) after 50 HIV-1 infections have been reported, whichever occurs earlier. The second evaluation by the IDMC will occur either (1) after 50% of participants have completed Week 48 (or prematurely discontinued from the study drug) or (2) after 100 HIV-1 infections have been reported, whichever occurs earlier. The third evaluation by the IDMC will occur either (1) after 50% of participants have completed Week 72 (or prematurely discontinued from the study drug) or (2) after 150 HIV-1 infections have been reported, whichever occurs earlier.

--	--

This study will be conducted in accordance with the guidelines of Good Clinical Practice (GCP) including archiving of essential documents.

GLOSSARY OF ABBREVIATIONS AND DEFINITION OF TERMS

Ab	antibody
AE	adverse event
Ag	antigen
AK	adenylate kinase
ALT	alanine aminotransferase
ANC	absolute neutrophil count
ANOVA	analysis of variance
ART	antiretroviral therapy
ARV	antiretroviral
AST	aspartate aminotransferase
AUC	area under the concentration versus time curve
BMD	bone mineral density
BUN	blood urea nitrogen
CASI	computer-assisted self-interview
CBC	complete blood count
CD4	cluster determinant 4
CDC	Centers for Disease Control and Prevention
CFR	Code of Federal Regulations
CI	confidence interval
CK	creatinine kinase
CL _{cr}	creatinine clearance
C _{max}	maximum observed concentration of drug
CNS	central nervous system
COVID-19	coronavirus disease 2019
CRF	case report form
CSR	clinical study report
C _{trough}	concentration at the end of the dosing interval
CYP	cytochrome P450
DBS	dried blood spot
DNA	deoxyribonucleic acid
DXA	dual-energy X-ray absorptiometry
E/C/F/TAF	elvitegravir/cobicistat/emtricitabine/tenofovir alafenamide (coformulated; Genvoya®)
EC	ethics committee
ECG	electrocardiogram
eCRF	electronic case report form
EDC	electronic data capture
eGFR	estimated glomerular filtration rate
ESDD	early study drug discontinuation

EU	European Union
F	emtricitabine (Emtriva®)
F/TAF	emtricitabine/tenofovir alafenamide (coformulated; Descovy®)
F/TDF	emtricitabine/tenofovir disoproxil fumarate
FAS	Full Analysis Set
FDA	Food and Drug Administration
FDC	fixed-dose combination
FTC	emtricitabine
FTC-TP	emtricitabine 5'-triphosphate
GCP	Good Clinical Practice
GFR	glomerular filtration rate
GGT	gamma glutamyltransferase
GI	gastrointestinal
Gilead	Gilead Sciences
GLPS	Global Patient Safety
HBcAb	hepatitis B virus core antibody
HBsAb	hepatitis B virus surface antibody
HBsAg	hepatitis B virus surface antigen
HBV	hepatitis B virus
HCV	hepatitis C virus
HDL	high-density lipoprotein
HDPE	high-density polyethylene
HIV	human immunodeficiency virus
HIV-1	human immunodeficiency virus type 1
HIV-2	human immunodeficiency virus type 2
IB	investigator's brochure
ICF	informed consent form
ICH	International Council for Harmonisation (of Technical Requirements for Pharmaceuticals for Human Use)
IDMC	independent data monitoring committee
IEC	independent ethics committee
IMP	Investigational Medicinal Product
IRB	institutional review board
IV	intravenous
IXRS	interactive voice/web response system
LDH	lactate dehydrogenase
LDL	low-density lipoprotein
LOCF	last observation carried forward
MSM	men who have sex with men
NA	not applicable

NOAEL	no observed adverse effect level
NRTIs	nucleotide reverse transcriptase inhibitors
OL	open label
PBMC	peripheral blood mononuclear cell
PBO	placebo
PCR	polymerase chain reaction
PD	pharmacodynamics
PEP	postexposure prophylaxis
PI	principal investigator
PK	pharmacokinetics
PP	Per Protocol
PrEP	pre-exposure prophylaxis
PRT	proximal renal tubulopathy
PT	Preferred Term
PY	person years
QT	electrocardiographic interval between the beginning of the Q wave and termination of the T wave, representing the time for both ventricular depolarization and repolarization to occur
QTc	QT interval corrected for heart rate
RBC/HPF	red blood cells per high power field
RBP	retinol-binding protein
RNA	ribonucleic acid
SAE	serious adverse event
SD	standard deviation
SDV	source data verification
SHIV	simian/human immunodeficiency virus
SOC	System Organ Class
SOP	standard operating procedure
STB	Stribild®
STI	sexually transmitted infection
SUSAR	suspected unexpected serious adverse reaction
TAF	tenofovir alafenamide
TDF	tenofovir disoproxil fumarate
TFV	tenofovir
TFV-DP	tenofovir diphosphate
TGW	transgender women
ULN	upper limit of normal
UNAIDS	United Nations Programme on HIV/AIDS
UP	urine protein
UPCR	urine protein to creatinine ratio

URAI unprotected receptive anal intercourse
US United States

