8.6. Statistical Testing Procedure

The primary hypothesis of non-inferiority of F/TAF relative to F/TDF, with respect to the incidence of HIV-1 infection rate per 100 PY will be tested first. Non-inferiority test will be performed at one-sided, 0.025 alpha level. Multiplicity adjustments for safety endpoints will be performed at Week 48 of the blinded phase with a fallback procedure {[Wiens 2005](#)} in the sequential order given below with pre-specified two-sided alpha levels:

- a) Hip BMD ($\alpha = 0.02$)
- b) Spine BMD ($\alpha = 0.01$)
- c) Renal biomarkers ($\alpha = 0.02$)

CCI

CCI

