8.8. Sample Size

A sample size of 2500 in each arm (1:1 randomization) provides at least 82% power to show F/TAF is non-inferior to F/TDF with respect to the HIV-1 infection rate. In this power analysis, a HIV-1 infection rate of 1.44 per 100 PY in the F/TAF and F/TDF treatment arms, a 2-sided Type 1 error rate of 5%, a non-inferiority margin of 1.62, and an average follow up of 2 years are assumed.

The non-inferiority margin of 1.62 and HIV-1 infection rate of 1.44 per 100 PY are based on an equal weighting approach using 3 historical studies of F/TDF versus placebo/untreated arms in MSM populations that are very similar to the population intended for this study (see [Table 8-1](#) below; the NI margin of 1.62 per 100 PY is the square-root of the lower bound of the 95% CI (2.64) of rate ratio to preserve 50% of treatment effect). The largest of the 3 studies is the IPREX study and the unprotected receptive anal intercourse (URAI) subgroup of the IPREX study is a high-risk population similar to the intended population of this study. Equal weighting for the 3 studies gives relatively more weight to the 2 smaller contemporary studies (PROUD and IPERGAY) than the alternative method of inverse variance weighting, thus providing an

estimate that is likely to be closer to the true estimate of F/TDF efficacy for PrEP. PROUD and IPERGAY were conducted when F/TDF was already established as an effective PrEP medication and represent the status for participants in the proposed study. IPREX, the largest and earliest of these 3 studies, was conducted when the effectiveness of F/TDF for PrEP was not established; thus, patients were informed of the unproven efficacy of F/TDF, which likely contributed to the much lower adherence rate in the IPREX trial. In contrast, PROUD and IPERGAY are more recent studies and were conducted after F/TDF was approved for prevention of HIV in a similar risk population, and likely contributed to the much higher adherence rate reported.

Table 8-1. Efficacy Information from Truvada as PrEP in MSMs

Clinical Trial	Sample Size Placebo (PY Follow-Up)	Sample Size F/TDF (PY Follow-Up)	HIV Infections (Incidence per 100 PY [95% CI])		Rate Ratios in HIV Infection Rates, per 100 PY [95% CI]	Enrollment
			PBO	F/TDF		
IPREX (URAI subgroup) at screening	753 (1054)	732 (1055)	56 (5.3) [4.0, 6.8]	23 (2.2) [1.4, 3.2]	2.4 [1.5, 3.9]	July 10, 2007 - Dec 17, 2009

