# 1.3. Sample Size and Power

### 1.3.1. Sample Size and Power (Protocol Pre-specified)

A sample size of 2500 in each arm (1:1 randomization) provides at least 82% power to show F/TAF is non-inferior to F/TDF with respect to the HIV-1 infection rate. In this power analysis, a HIV-1 infection rate of 1.44 per 100 person-years (PY) in the F/TAF and F/TDF treatment arms, a 2-sided Type 1 error rate of 5%, a non-inferiority margin of 1.62, and an average follow-up of 2 years (ie, last subject has a minimum of 48 weeks of follow-up and at least 50% of the subjects have at least 96 weeks of follow-up after randomization) are assumed.

The non-inferiority (NI) margin of 1.62 and HIV infection rate of 1.44 per 100 PY are based on an equal weighting approach using three historical studies of F/TDF versus placebo/untreated arms in MSM populations that are very similar to the population intended for this study (see Table 1-1 below; the NI margin of 1.62 per 100 PY is the square-root of the lower bound of the 95% CI (2.64) of rate ratio to preserve 50% of treatment effect). The largest of the three studies is the iPrEX study and the unprotected receptive anal intercourse (URAI) subgroup of the iPrEX study is a high-risk population similar to the intended population of this study. Equal weighting for the three studies gives relatively more weight to the two smaller contemporary studies (PROUD and IPERGAY) than the alternative method of inverse variance weighting, thus providing an estimate that is likely to be closer to the true estimate of F/TDF efficacy for PrEP. PROUD and IPERGAY were conducted when F/TDF was already established as an effective PrEP medication and represent the status for subjects in the proposed study. iPrEX, the largest and earliest of these three studies, was conducted when the effectiveness of F/TDF for PrEP was not established; thus, participants were informed of the unproven efficacy of F/TDF, which likely contributed to the much lower adherence rate in the iPrEX trial. In contrast, PROUD and IPERGAY are more recent studies and were conducted after F/TDF was approved for prevention of HIV in a similar risk population, which likely contributed to the much higher adherence rate reported.

	Sample Size	Sample Size	HIV Ir (Incidence ple Size [95%		Rate Ratios in HIV Infection Rates, per	
Clinical Trial	Placebo (PY Follow Up)	F/TDF (PY Follow Up)	PBO	F/TDF	100 PY [95% CI]	Enrolment

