# Appendix Figure 4. Power for Superiority Test against Historical Placebo

Assuming 4250 PY follow up per arm (based on estimated follow up time by the time of the primary analysis).

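### The 48/96-week analysis trigger does not guarantee the 2-year average follow-up behind the stated 82% power; at the SAP's own estimate of 4250 person-years per arm, power is about 76%

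*Protocol*

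**What the plan says.** Protocol 8.8 states: "A sample size of 2500 in each arm (1:1 randomization) provides at least 82% power to show F/TAF is non-inferior to F/TDF". The inputs are a rate of 1.44 per 100 PY in both arms, a two-sided 5% error rate, and "a non-inferiority margin of 1.62, and an average follow up of 2 years are assumed". In that section the 2 years stands as a plain assumption.

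The synopsis (Statistical Methods) gives the same calculation but explains the follow-up figure: "an average follow up of 2 years (ie, last participant has a minimum of 48 weeks of follow up", together with the condition that at least half have 96 weeks. SAP 1.3.1 carries the same explanation: "an average follow-up of 2 years (ie, last subject has a minimum of 48 weeks of follow-up".

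The primary analysis is timed by those two conditions alone (Protocol 3.1.1, 8.1.2 and 8.4.1). None of these sections requires a mean follow-up, a person-year total or an event count.

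SAP Appendix 8, in the note to Appendix Figure 4, uses a different amount of follow-up for the same time point: "Assuming 4250 PY follow up per arm (based on estimated follow up time by the time of the primary analysis").

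**The concern.** 'Ie' tells the reader that the 2-year average and the 48/96-week trigger are the same thing, so that meeting the trigger delivers at least 82% power. A mean of about 104 weeks does not follow from minimums of 48 and 96 weeks. The SAP also holds two unreconciled figures for follow-up at the primary analysis: 5000 PY per arm implied by section 1.3.1 (2500 × 2 years) and 4250 PY per arm in Appendix 8, which is 15% lower.

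In an event-driven comparison, person-years determine power. If the follow-up at the trigger is below 2 years on average, the trial has a greater chance of failing to show a non-inferiority that is true, and the stated power overstates what was available.

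**Working it through.** **Inputs.** Rate 1.44 per 100 PY in both arms, so the true ratio is 1; margin 1.62; two-sided 5% (Protocol 8.6: "Non-inferiority test will be performed at one-sided, 0.025 alpha level"); 2500 per arm; Poisson model with log link (Protocol 8.4.1). Weeks are converted at 365.25 days per year, the year length the SAP uses in 6.2.1.

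**Formula.** With E expected events per arm, E = 0.0144 × PY, the log rate ratio has standard error √(2/E), and

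power = Φ( ln 1.62 / √(2/E) − 1.96 ), with ln 1.62 = 0.482.

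**The plan's own figure.** 2500 × 2 = 5000 PY and E = 72. Then 0.482/√(2/72) − 1.96 = 0.935, and Φ(0.935) = 82.5%. The stated 82% reproduces.

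**What the trigger guarantees.** The minimum is half at 96 weeks and half at 48 weeks: 0.5 × 96 + 0.5 × 48 = 72 weeks, or 1.38 years. 2500 × 72 × 7/365.25 = 3450 PY.

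**What even accrual gives.** If accrual is uniform over no more than 96 weeks and the analysis falls when half reach Week 96, those above and below balance and the mean is 96 weeks, or 1.84 years. 2500 × 96 × 7/365.25 = 4600 PY. Even accrual is an assumption. SAP Appendix 9 gives enrolment from September 2016 to June 2017, at most about 43 weeks.

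**Results per arm, no dropout in the rows derived from 2500 per arm.**

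| Basis | PY | Events | Power (formula) | Power (simulated Poisson Wald 95% CI) |
|---|---|---|---|---|
| 2-year mean | 5000 | 72.0 | 82.5% | 82.1% |
| 96-week mean, 2500 per arm | 4600 | 66.2 | 79.3% | 78.8% |
| SAP Appendix 8 estimate | 4250 | 61.2 | 76.1% | 75.7% |
| Trigger minimum, 2500 per arm | 3450 | 49.7 | 67.2% | 66.6% |

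**What the stated power requires.** For 82%: E = 2 × ((1.96 + 0.915)/0.482)² ≈ 71.0 events, and 71.0/0.0144 ≈ 4934 PY per arm, a mean of 1.97 years on 2500. For 80%: about 67.4 events, or 4684 PY. The 4250 PY estimate falls short of both.

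**Effect of over-enrolment.** SAP Appendix 3 gives 5387 in the Safety Analysis Set, about 2694 per arm. If all averaged 96 weeks with no loss, 2693.5 × 96 × 7/365.25 = 4956 PY and power is 82.2%. By comparison, 4250 PY is 4250/2500 = 1.70 years per participant, or 4250/2693.5 = 1.58 years.

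Using the adjusted alpha of 0.04997 from SAP 3.5 moves none of these results by more than 0.1 percentage point.

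**The case against.** The best reply is that nothing was miscalculated. The 82% is right for its stated inputs, the 2 years is called an assumption, and the full power section in Protocol 8.8 has no gloss. The trigger consists of minimums, so it is compatible with a 2-year mean: uniform accrual over 120 weeks would give 2.07 years and 83.8% power. This stands, but only for Protocol 8.8. The synopsis and SAP 1.3.1 do not say compatible; they say 'ie'. With enrolment of at most about 43 weeks, that slow-accrual case is not this trial.

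Second, the 67% does not describe what happened. With enrolment that short, the last participant would be at about 96 − 43 = 53 weeks or more when half reach Week 96, and more than 2500 per arm were treated. This is fair: 67% is the trigger's guaranteed floor at the planned size, not a forecast.

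Third, the 4250 PY comes from a note to a figure about superiority over a historical placebo, with no sample size or dropout handling given. That limits what can be attributed to 2500 per arm. It does not make the number irrelevant: it is described as the estimated follow-up at the primary analysis, and person-years per arm are the same whichever test uses them.

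Fourth, full over-enrolment with a 96-week mean and no loss restores 82.2%. That is correct, but it needs zero loss, no dropout allowance is stated, and SAP 2.2 words the trigger so that early discontinuation also satisfies it. It also does not match the SAP's own lower estimate.

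Finally, the shortfall need not carry into the end-of-blinded-phase analysis that this SAP governs, because follow-up then continues until the last subject reaches Week 96. Even accrual over about 40 weeks would give a mean of 96 + 20 = 116 weeks: 2500 × 116 × 7/365.25 = 5558 PY and about 86% power without dropout. This also stands. The point concerns the power stated for the primary analysis.

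**Conclusion.** The concern holds. The 82% is correctly computed for 5000 PY per arm, but the synopsis and SAP 1.3.1 wrongly equate that follow-up with the 48/96-week trigger. At 2500 per arm without dropout, the trigger guarantees 67% power and even accrual gives about 79%. At the SAP's estimated 4250 PY per arm, power is about 76%, some 6 points below the stated figure. The risk of missing true non-inferiority is then about 24%, against 17.5% at 5000 PY.

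These figures assume equal rates of 1.44 per 100 PY and the Wald approximation, which simulation supports to within about 0.6 point. The 76% belongs to 4250 PY, not to 2500 per arm, because the SAP does not say which sample size underlies that estimate. SAP section 1 reports the primary analysis as complete, so the consequence is for reporting and interpretation only.

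**What to change.** Delete the parenthesis beginning 'ie' from the synopsis power statement and from SAP 1.3.1. In those two places and in Protocol 8.8, label the 2-year average as a planning assumption that makes no allowance for dropout. Then add a sentence such as: 82% power requires about 71 events (about 4934 PY) per arm at 1.44 per 100 PY; at the 4250 PY per arm estimated for the primary analysis in SAP Appendix 8, power is about 76%. Identify the second figure as a later estimate, so that it is not read as part of the prespecified calculation, and express it by person-years rather than as the power of 2500 per arm.

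The cost is a text correction in three places and a stated power that becomes conditional on person-years and less favourable at the SAP's own estimate. Enrolment, margin and analysis are unchanged.
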